4.2.3. Vital Signs

Summary table for change from baseline of Vital Signs will be produced. Listing of all Potential Clinical Important abnormalities will be presented (see Section [6.2.1](#)).

4.2.4. ECG

Summary tables for ECG findings and change from baseline of 12-Lead ECG will be produced. Maximum QTcF (Friderica's QT Interval Corrected for Heart Rate) values post-baseline relative to baseline will be produced and will be used to detect any clinical important changes. The categories are defined as:

- Maximum QTcF values at post baseline relative to baseline:
 - To <=450 msec or No Change
 - Any Increase, To >450 to <=480 msec
 - Increase To >480 to <=500 msec
 - Increase To >500 msec
- Maximum increase in QTcF values post baseline relative to baseline:
 - Increase <=30 msec
 - Increase of 31-60 msec
 - Increase of >60 msec

Listing of all Potential Clinical Important abnormalities will be presented (see Section [6.2.1](#)).

Full details of the planned safety displays are provided in the Output and Programming Specification (OPS).

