7.2.2. QTc Criteria

QTc study stopping criteria, and individual participant increased monitoring criteria, have been designed to assure participant safety. The same QT correction formula must be used for each individual participant to determine eligibility for and discontinuation from the study. Use of Fridericia's formula (QTcF) is preferred in this study. The formula may not be changed or substituted once the participant has been enrolled; for example, if a participant is eligible for the protocol based on QTcF, then QTcF must be used for discontinuation of this individual participant as well. Safety ECGs and other non-protocol specified ECGs are an exception.

Participants that meet either of the bulleted criterion below, additional monitoring will be undertaken until the QTc value is no longer clinically significant. The frequency of this monitoring and the decision as to when the QTc value is no longer clinically significant will be at the discretion of the Investigator. The participant should continue in the study, given this is a single dose study.

- QTcF >500 msec.
- Change from baseline: QTc >60 msec.

If a single ECG demonstrates a prolonged QTc interval, then a further two ECG readings should be obtained over a brief recording period (e.g., 5-10 minute) and the averaged QTc interval used to determine whether the participant meets the criteria to trigger further monitoring.

If a participant meets any of the criteria above, this will result in review by the GSK DEC before further participants are dosed.

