6.2.5. Multiple measurements at One Analysis Time Point

When multiple assessments are taken, the mean of the measurement will be calculated first and summary statistics will be based on the calculated mean. This will apply to both baseline and post baseline assessments.

For lab tests on a study day, if multiple assessments are taken, the worst case will be used.

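### The QTcF increase categories in SAP 4.2.4 have no row for averaged increases between 30 and 31 msec, although SAP 6.2.2 flags them as above 30 msec

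*SAP*

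**What the plan says.** SAP 4.2.4 (ECG) defines a categorical display headed "Maximum increase in QTcF values post baseline relative to baseline". Its rows are "Increase <=30 msec", "Increase of 31-60 msec" and "Increase of >60 msec". The absolute QTcF categories just above it use contiguous limits: >450 to <=480, >480 to <=500 and >500 msec.

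SAP 6.2.5 sets the rule for replicates: "When multiple assessments are taken, the mean of the measurement will be calculated first and summary statistics will be based on the calculated mean". It adds: "This will apply to both baseline and post baseline assessments". The worst-case exception in that section is for laboratory tests, not ECGs.

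SAP 6.2.2 gives the flag for potential clinical importance as a QTcF increase from baseline of >30 msec, with no step to the next whole number. SAP 4.2.4 also plans change-from-baseline summaries and a listing of flagged ECG abnormalities, and refers to the Output and Programming Specification for display details.

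The ECG rows of the protocol's schedules of activities decide who has replicates. SC cohorts (Section 1.3.3) have triplicates pre-dose and at PK timepoints during the inpatient stay, then single readings at outpatient visits. IV cohorts (Section 1.3.2) have single readings pre-dose and at PK timepoints, with a triplicate only when a clinically significant finding is suspected.

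**The concern.** The first row closes at 30 and the second opens at 31. That covers every case only if every change is a whole number. The SAP's own averaging rule, applied to planned triplicates, produces changes in thirds of a msec, and the visible SAP states no rounding rule for QTcF.

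ECG change is part of the primary safety endpoint, and SAP 4.2.4 says the maximum-QTcF outputs will be used to detect clinically important changes. For a participant in the gap, two outputs from the same SAP would disagree: flagged under 6.2.2, counted in no row under 4.2.4. The row counts would then fall short of the number assessed.

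**Working it through.** The plan gives no figure to reproduce. The check applies the rows literally and then sizes the gap.

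**1. Which changes are possible.** Assume the ECG machine reports whole msec; the documents do not state its resolution.
- Single reading minus single reading: the change D is an integer. No integer lies strictly between 30 and 31, so nothing is lost.
- A triplicate mean at baseline, after dosing, or both: D = k/3 for an integer k. The gap 30 < k/3 < 31 requires 90 < k < 93, so k = 91 or 92 and D = 30.33 or 30.67 msec.
- Upper boundary: 60.33 msec already falls in the >60 row, so there is no gap at 60.

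**2. Example.** Baseline readings 400, 400 and 401 have mean 1201/3 = 400.33. Post-dose readings 431, 431 and 431 have mean 431.00. The increase is 431.00 − 400.33 = 30.67 msec. It is above 30 and below 31, so it has no row, but it exceeds the >30 flag in SAP 6.2.2.

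**3. Would rounding settle it?** Rounding to whole msec puts 30.67 in the 31-60 row, but puts 30.33 in the <=30 row while SAP 6.2.2 flags it as >30. The outputs would still disagree for that value.

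**4. Who is exposed by design.** SAP 4.1.3 takes the latest pre-dose value as baseline. In IV cohorts that is the single pre-dose reading on Day 1, not the screening triplicate. SAP 1.2 lists cohorts 3 and 5 as the SC cohorts, with eight participants each: 2 × 8 = 16. IV participants are exposed only if a reading happens to be repeated in triplicate.

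**5. Size.** Simulation of the largest of 12 post-dose changes from the mean of three whole-msec baseline readings. Assumptions: normal, independent readings; no drug effect; within-person SD of 8, 10 or 12 msec. The SD and the number of visits are assumed, not taken from the documents.

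| SD (msec) | P(gap), single post-dose readings | Expected of 16 | P(gap), triplicate post-dose readings | Expected of 16 |
|---|---|---|---|---|
| 8 | 0.0015 | 16 × 0.0015 = 0.02 | 0.0000 | 0.00 |
| 10 | 0.0066 | 16 × 0.0066 = 0.11 | 0.0003 | 16 × 0.0003 = 0.005 |
| 12 | 0.0138 | 16 × 0.0138 = 0.22 | 0.0021 | 16 × 0.0021 = 0.03 |

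SC participants have a mix of the two types of post-dose reading, so the relevant figure lies between the two columns for each SD.

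**6. After the fix.** With <=30, >30 to <=60 and >60, every value from −30 to +90 msec, in steps of 1 or 1/3 msec, falls in exactly one row. Both 30.33 and 30.67 move to the middle row, in agreement with SAP 6.2.2.

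**The case against.** The strongest reply is that 31-60 is ordinary whole-msec shorthand, and that the Output and Programming Specification, which is not available here, may round or use contiguous limits. That cannot be excluded. However, the SAP does not say so, it uses contiguous limits for absolute QTcF in the same section, and simple rounding would still leave 30.33 at odds with the >30 flag.

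A second reply is that nothing depends on this row. That stands. Protocol 9.4.3 plans no formal testing of safety data and makes investigator-reported relationship of adverse events the principal consideration. The criteria in Protocol 7.2.2 that lead to extra monitoring and committee review are QTcF >500 msec and a change >60 msec.

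A reader might also infer that suspicious readings are the ones most often averaged, so the gap sits where it does most harm. The documents do not support this. Protocol 7.2.2 does have "the averaged QTc interval used to determine whether the participant meets the criteria to trigger further monitoring", but that follows a single ECG with a prolonged QTc and serves the >500 and >60 criteria. No protocol rule calls for a repeat at a 30 msec increase. The main source of fractional values is the planned SC triplicates.

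**Conclusion.** The rows are wrong as written, with a very small effect. Two stronger readings fail. First, a reader might infer that the participant disappears from the report. In fact the participant is missing from one category table only, and remains in the listing of flagged values and the change-from-baseline summaries. Second, a reader might infer that all 54 participants are exposed. IV pre-dose and scheduled readings are single, so planned exposure is the 16 SC participants, with at most about 0.2 expected in the gap at the largest SD considered.

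That figure rests on the assumed SD of 8 to 12 msec, 12 visits, no drug effect and whole-msec readings. A drug effect on QTcF, more post-dose readings or a larger SD would change it. If QTcF were recorded with decimals, single readings in the IV cohorts could fall in the gap too. The existence of the gap, and the correction, do not depend on the size.

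**What to change.** In SAP 4.2.4, replace the three rows for maximum QTcF increase with <=30 msec, >30 to <=60 msec and >60 msec. This matches the contiguous limits already used for absolute QTcF in that section and the >30 msec flag in SAP 6.2.2. Carry the same limits into the Output and Programming Specification, applied to the unrounded change. The cost is one SAP line and the matching programming labels; no new data or analysis is needed and trial conduct is unaffected.

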4.3. Secondary Endpoint(s) Analyses

The secondary objectives of this study are to evaluate the Pharmacokinetics, Immunogenicity, Target Engagement (TE) and Pharmacodynamic biomarkers.

4.3.1. Pharmacokinetic Analyses

The PK analyses will be performed by, or under the direct auspices of GSK Biostatistics, as well as Clinical Pharmacology Modelling and Simulation (CPMS).

4.3.1.1. Definition of endpoint(s)

- Serum PK concentrations
- PK Parameters as data permits:
 - Area under the Concentration-time curve CCI [REDACTED]
 - CCI [REDACTED]
 - Maximum Concentration [Cmax]
 - Time to Cmax [Tmax]
 - Half-life [$t^{1/2}$]
 - CCI [REDACTED]
 - Clearance [CL or CL/F (SC cohorts)]
 - CCI [REDACTED]
 - [REDACTED]
 - [REDACTED]
 - [REDACTED]
 - [REDACTED]
 - [REDACTED]

4.3.1.2. Main analytical approach

Serum PK concentrations are assumed to be log-normally distributed and appropriate summary statistics will be displayed (see Section 4.1.1) by study intervention over time. Plots of individual concentration and median concentration data with range over time will be produced by GSK Biostatistics.

PK parameters will be calculated by standard non-compartmental analysis using the current supported version of WinNonlin by CPMS and transferred back to GSK Biostatistics to provide descriptive statistics. All calculations of non-compartmental parameters will be based on actual sampling times.

The untransformed and \log_e transformed PK Parameters will be summarized separately. Appropriate summary statistics will be displayed (see Section 4.1.1) as follows:

- Untransformed PK parameter variables: Tmax, CCI [REDACTED] ■ [REDACTED]

- Log_e transformed PK parameter variables: AUC [redacted], Cmax, Clearance [CL or CL/F (SC cohorts)], [redacted] and Half-life (t_{1/2})

4.3.2. Immunogenicity Analyses

The immunogenicity analyses will be based on the Safety Analysis Set.

Immunogenicity testing involves a screening assay and a confirmation assay that together produce 3 results:

- Screening assay result (positive / negative)
- Confirmatory assay result (positive / negative) if positive result in the screening assay
- Titre result (numeric) if positive result in the confirmation assay

The immunogenicity analyses will be summarised by incidence, i.e., the number of participants with anti-drug antibodies by study intervention over time and the titre of immunogenicity results will be listed.

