1.3.2. Intravenous Dosed Cohorts

Procedure	CCI	Intervention Period (Days) for IV cohorts												Notes
		1	2	3	4	5	6	7	8	9	10	11	12	
Randomization	X													
Urinalysis (Dipstick ±microscopy)		X		X	X	X	X	X	X	X	X	X		If dipstick is positive or participant has urinary symptoms send for microscopy. CCI [REDACTED]
Study Intervention Administration (IV)	X													
Discharge			X											
SARS-CoV-2 Test		<=====>												As per local guidelines.
Brief Physical Exam			X										X	
Laboratory assessments (include clinical chemistry, and haematology panels)		X		X	X	X	X	X	X	X	X	X		
CD4+ T cell counts	X				X		X	X	X	X	X	X		
CCI														
Viral quantification and serology (EBV, CMV and VZV)	X						X					X		Day 1 collection prior to administration of study intervention.
12-lead ECG	X	X	X	X	X	X	X	X	X	X	X	X		Single readings to be recorded pre-dose and at PK timepoints. Performed in triplicate if suspected clinically significant findings.
CCI														

Procedure	CCI	Intervention Period (Days) for IV cohorts													Notes
		X	X	X	X	X	X	X	X	X	X	X	X	X	
Vital signs		X	X	X	X	X	X	X	X	X	X	X	X	X	Day 1 vitals to be taken pre-dose and end of IV infusion and at CCI [REDACTED] from start of IV dosing on Day 1.
Blood collection for Pharmacokinetics		X	X	X		X	X	X	X	X		X	X		Day 1 PK samples to be collected prior to, midpoint and end of IV infusion, and at CCI [REDACTED] post-start of IV dosing.
Blood collection for Target Engagement (TE) biomarkers		X	X	X		X	X	X	X	X		X	X		Day 1 TE samples to be collected prior to and at CCI [REDACTED] post-start of IV dosing.
Blood collection for Immunogenicity		X							X		X		X	X	Day 1 collection prior to administration of study intervention
CCI			X		X		X	X		X			X		Day 1 collection prior to administration of study intervention
Blood collection for cellular biomarkers		X		X		X	X		X		X		X		Day 1 collection prior to administration of study intervention
CCI		X				X				X					Day 1 collection prior to administration of study intervention
AE Review															
SAE Review															
Concomitant medication review															

Procedure	CCI	Intervention Period (Days) for IV cohorts	Notes
CCI	CCI		

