9.4.4.3. Other Safety Analyses

The analyses will be based on “Safety” analysis set.

Immunogenicity data will be summarized as the number and percentage of participants with confirmed positive anti-GSK3888130B antibodies and where applicable the titres will be listed.

CCI

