1.1. Objectives and Endpoints

Objectives	Endpoints
Primary	
To investigate the safety and tolerability of single IV and SC doses of GSK3888130B in healthy participants.	
 • Occurrence of Adverse Events (AEs) and Serious Adverse Events (SAEs). • Occurrence of clinically significant changes in laboratory values (CD4⁺ T cell counts, haematology, chemistry, urinalysis and virology), vital signs and 12lead electrocardiogram (ECG) readings.
Secondary	
To characterise the serum PK profile of single IV or single SC doses of GSK3888130B in healthy participants.	Serum concentrations of GSK3888130B and derived PK parameters as data permit, including area under the concentration-time curve [AUC], maximum concentration [Cmax], time to Cmax [Tmax], half-life [t _{1/2}], clearance [CL].
To evaluate the immunogenicity of single doses of GSK3888130B in healthy participants.	Incidence of Anti-Drug Antibodies (ADAs) against GSK3888130B.
To characterise the effects of GSK3888130B on target engagement (TE).	Change from baseline in derived free IL-7 levels (calculated from total IL-7 assay measurements) over time.
To characterise the effect of single doses of GSK3888130B on PD biomarker Bcl-2.	Change from baseline in T cell Bcl-2, measured in blood over time.
Tertiary/Exploratory/Other	
CCI	

Objectives	Endpoints
CCI	

Objectives	Endpoints
CCI	

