4. STATISTICAL ANALYSES

4.1. General Considerations

4.1.1. General Methodology

Participants who prematurely withdraw from study may be replaced.

Unless otherwise specified, the Screened, Enrolled, Randomised or Safety Analysis Sets will be used for all Study Population analyses, the Safety Analysis Set will be used for all Safety analyses, the PK Analysis Set will be used for all Pharmacokinetic analyses and the PD Analysis Set will be used for all Pharmacodynamic/ Biomarker analyses.

For all summaries, statistical analyses and plots, Placebo participants will be pooled across all cohorts in which the endpoint was collected, except for the following endpoints:

- Cellular Biomarkers, CCI [REDACTED] and CCI [REDACTED] (Section 4.4.3): Placebo data will be pooled across Cohorts 1,2,3,4 and 7 CCI [REDACTED]
[REDACTED]
[REDACTED].
- CCI [REDACTED] Placebo data will be summarised by cohort since there are limited timepoints relative to the CCI [REDACTED] which are common to these cohorts.

CCI [REDACTED]
[REDACTED]
[REDACTED]

CCI [REDACTED]
[REDACTED]

Absolute baseline values will be included in all change from baseline or ratio to baseline summaries. Line plots will be produced on absolute values unless otherwise specified.

95% equal tailed Credible Intervals (CrI) will be used for statistical analyses unless otherwise specified.

Summary tables will provide the following descriptive statistics as a minimum, unless otherwise specified:

- For continuous untransformed data (or where many zeros exist in the data): n, mean, 95% Confidence Intervals (CI), standard deviation (SD), median, minimum and maximum. Number of Zeros may also be added as an additional statistic, if deemed appropriate.
- For continuous log-normally distributed data: n, geometric mean, 95% CI of the geometric mean, standard deviation on the log scale (SD (log)), %CVb (only for PK Parameters), median, minimum and maximum.
- For categorical data: number and percentage of participants in each category.

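### SAP 4.3.2 reports ADA incidence without using the scheduled pre-dose sample, so a persistent pre-dose positive counts the same as a treatment-induced case

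*SAP*

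**What the plan says.** The secondary objective is to evaluate the immunogenicity of single doses, and the endpoint is "Incidence of Anti-Drug Antibodies (ADAs) against GSK3888130B" (SAP 1.1; protocol section 3 agrees).

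SAP 4.3.2 describes a screening assay, a confirmatory assay and a titre for confirmed positives. It then sets the summary as "the number of participants with anti-drug antibodies by study intervention over time", and adds that "the titre of immunogenicity results will be listed". On the population it says "The immunogenicity analyses will be based on the Safety Analysis Set", which covers active and placebo participants.

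Protocol 9.4.4.3 plans "the number and percentage of participants with confirmed positive anti-GSK3888130B antibodies". It does not restrict this to post-dose samples and does not mention pre-dose status.

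The immunogenicity row of the IV schedule (protocol 1.3.2) carries the note "Day 1 collection prior to administration of study intervention". The SC schedule (protocol 1.3.3) has the same note.

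Two general SAP rules bear on the point. SAP 4.1.1 gives the default "For categorical data: number and percentage of participants in each category". SAP 6.2.4 adds a worst-case post-baseline row to by-visit summaries, with unscheduled visits included in its derivation.

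**The concern.** Incidence, in its ordinary sense, counts new cases after exposure. The number of participants positive at each time point is prevalence at that time point. The two differ when someone is reactive before dosing.

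The plan collects what is needed to tell these cases apart: a pre-dose sample, later samples, and a titre for each confirmed positive. The visible text never uses them together. SAP 4.1.3 defines a baseline for all endpoints, and SAP 4.1.3.1 uses it for differences, ratios and fold changes. Neither classifies a positive or negative ADA result by its pre-dose status. There is also no rule for a pre-dose positive whose titre rises, and no denominator specific to ADA.

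What is at stake is the reading of a secondary endpoint in very small dose groups, where a single participant moves the percentage a long way. The immunogenicity summary also goes to the Dose Escalation Committee at the first interim analysis (protocol 9.5; SAP 4.7, Table 3).

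**Working it through.** The documents give no ADA rate, precision or sample-size figure, so there is nothing of the plan's own to reproduce. The check compares the rules and then illustrates their effect.

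**Inputs**
- Cohorts 1 and 2: 5 participants each at 3:2, so 3 active each (SAP 1.2).
- Cohorts 3, 4, 5 and 7: 8 each at 3:1, so 6 active each (SAP 1.2).
- Cohort 6: an exception whose details are redacted. By subtraction, 54 − 2×5 − 4×8 = 12. At 3:1 this would be 9 active.
- Total active: 2×3 + 4×6 + 9 = 39. Using the 14 placebo participants in SAP section 5 instead, 54 − 14 = 40. I use roughly 40.
- Pre-existing reactivity p: not in the documents. Assumed 2%, 5% and 10%, independent between participants.

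**Effect of one persistent pre-dose positive on the reported percentage**
- Group of 6: 1/6 = 17 percentage points.
- Group of 3: 1/3 = 33 percentage points.

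**How likely this is**

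Chance of at least one pre-dose positive among 6 active participants = 1 − (1 − p)^6. Expected number among 40 active = 40p.

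| Assumed p | 1 − (1 − p)^6 | 40p |
|---|---|---|
| 2% | 0.114 (11%) | 0.8 |
| 5% | 0.265 (26%, from 0.2649) | 2.0 |
| 10% | 0.469 (47%) | 4.0 |

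These are participants positive before dosing. Only those still confirmed positive after dosing enter a post-dose count, so the figures are upper limits on the number miscounted.

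**Worked example (illustrative)**

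Take 6 active participants, a pre-dose sample and four post-dose samples. One is positive before dosing and stays positive with an unchanged titre. Two others become positive, each at one visit, and at different visits.
- Rows over time: 1, 1, 2, 2, 1 of 6.
- Worst-case post-baseline row, if applied to ADA: 3/6 = 50%.
- Overall confirmed positives as in protocol 9.4.4.3: also 3/6.
- New responses: 2 participants. That is 2/6 = 33% of those with pre-dose and post-dose results, or 2/5 = 40% of those negative before dosing.

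The any-visit figure exceeds the treatment-emergent figure by 50% − 33% = 17 points. Two of the by-visit rows also read 2/6, but each mixes one old case with one new one.

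**Rules side by side**

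| Rule | Any post-dose visit? | Separates pre-dose positives? |
|---|---|---|
| SAP 4.3.2, over time | Not stated | No |
| SAP 6.2.4, worst case | Yes, if applied to ADA | No |
| Protocol 9.4.4.3 | Possibly; no time restriction | No |
| SAP 4.1.3 and 4.1.3.1 | Not applicable | No; value changes only |

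**The case against.** The strongest case against is that much of what is needed is already planned. If ADA is summarised by visit, SAP 6.2.4 adds a worst-case row, and the natural worst case for a positive/negative result is positive at any post-dose visit. Protocol 9.4.4.3 plans an overall number and percentage. Day 1 results would show pre-existing positives, listings would let a reader follow an individual, and pooled placebo shows background reactivity. Detailed displays sit in the Output and Programming Specification, which is not available here, and part of the SAP's derivation appendix is redacted. Neither document defines incidence as treatment-emergent.

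Much of this stands. A reader might infer that the plan gives no per-participant count at all and so cannot estimate its endpoint. The documents do not support that: SAP 6.2.4 and protocol 9.4.4.3 may each supply an any-visit count, although SAP 4.3.2 does not say so. A reader might also infer that every pre-dose positive is carried forward as positive at each later visit. That is not what SAP 4.3.2 says, since a sample needs a positive screening result and then a positive confirmatory result.

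The objection does not close the gap. An any-visit count still includes a pre-dose positive who stays positive. A Day 1 total does not link one person's results before and after dosing, and placebo gives only an average background. A listing permits a later derivation, but leaves the boost threshold and the denominator to be chosen after results are seen.

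**Conclusion.** The point holds, limited to the handling of pre-dose positives. As written, the ADA summary can count pre-existing reactivity as a response to the drug, and no visible rule in either document prevents this. The error is 17 percentage points per persistent pre-existing positive in an active group of 6, and 33 in a group of 3.

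The probabilities rest on assumed rates of 2% to 10%, and the expected counts also on roughly 40 active participants. Applying those rates to all 54 would overstate the matter, because placebo reactivity measures background and does not inflate the active groups.

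The conclusion also rests on the ordinary meaning of incidence and on reading "the number of participants with anti-drug antibodies by study intervention over time" as counts by visit. The endpoint is secondary and descriptive, no hypothesis is tested, and the right count could be derived from data already collected. The impact is modest, but the change is worth making.

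**What to change.** In SAP 4.3.2:
- Add, per study intervention, n/N (%) of participants with treatment-emergent ADA at any post-dose visit.
- Define it as pre-dose negative to confirmed post-dose positive, or a titre rise over pre-dose by a fold fixed in advance from assay variability.
- Define N as participants with a pre-dose result and at least one post-dose result.
- Show pre-existing ADA as its own row.
- Keep the by-visit table, say whether the worst-case row of SAP 6.2.4 applies to ADA, and align the summary with protocol 9.4.4.3.

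This costs one derived variable and one table. No new sampling is needed: the pre-dose samples are scheduled and titres of confirmed positives are already reported. The fold should be written down before results are seen.
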